Simple reaction time (SRT) test: Subjects will be assessed by an online-based test (<http://getyourwebsitehere.com/jswb/rttest01.html>). Each volunteer will be instructed to press the mouse button as soon as possible, when a stoplight displayed on a computer screen changes from red to green. During the four first study sessions, each volunteer will be tested at baseline (before administration of melatonin), and once every hour for 8 hours after administration of melatonin, as well as 24 hours after administration of melatonin. For the transdermal study session, the test will be performed at every hour on the first day until 16 hours, as well as at 24 and 48 hours.

Other adverse reactions include pre-specified self-reported symptoms of nervousness, confusion, depressed mood, dizziness, headache, garlic breath and burning sensation from application area (yes/no). Volunteers will also be asked to report additional symptoms of adverse reactions, if any (yes/no + description). Results will be noted in the CRF.

When the subjects are included, a set of baseline demographics data will be recorded in the CRF, including date of birth, ethnicity, weight, height, and BMI.

Subjects/population

Inclusion criteria:

- Healthy female
- 20-40 years old
- BMI 18-30

Exclusion criteria:

- Inability to understand Danish, written or spoken.

- Current use of melatonin or other hypnotics/sedatives
- Current pregnancy (a positive urine-HCG; the subjects will be tested prior to each study session)
- Breast feeding
- Current alcohol or drug abuse (defined as over 5 units of alcohol per day, or any usage of illegal drugs)
- Mental illness (defined as being in medical treatment)
- Serious comorbidity (American Society of Anesthesiologists (ASA) physical status 3-4)
- Participation in other clinical trials less than 1 month prior to current study
- Night-shift work within the last 14 days prior to study
- Planned night-shift work within the study period
- Known and diagnosed sleep-disorder (defined as being in current medical treatment)
- Plasma hemoglobin <7.8 mmol/L (measured when screening participants)

Withdrawal and dropout criteria

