DMSO is regularly used in the treatment of interstitial cystitis, either as monotherapy, or serving as a vehicle for anti-inflammatory agents [48-50]. DMSO has previously been applied as a solvent for intravesical drug administration in the treatment of bladder cancer [51, 52]. An adverse reaction of DMSO is a garlic-like breath odor and taste, due to pulmonary elimination of a small percentage of the DMSO as dimethyl sulfide. One study demonstrated that up to 48% of patients with interstitial cystitis reported adverse reactions, including urethral irritation and nausea [49]. However, these adverse reactions are self-limiting, lasting up to 24-48 hours [48-50].

Adverse reactions of glycofurol

Glycofurol has previously been used as a solvent for rectal administration of methadone [53, 54]. Furthermore, glycofurol is used as an ingredient in Stesolid® (diazepam) rectal fluid [55]. Glycofurol is generally perceived as a non-toxic and non-irritant material, being nevertheless irritating if injected undiluted [56]. In this study, the glycofurol will be diluted to a 20% w/w

glycofurol and 40% w/w DMSO in water, the solution containing 10 mg/g melatonin. Therefore any irritating effects from the glycofurol should be avoided.

Adverse effects of plasma sampling

During the study a total of 136 ml of blood will be sampled from the subjects per study session the first four study sessions (intravenous, rectal, intravesical, and vaginal). A total of 122 ml of blood will be sampled from the subject during the transdermal study session. The drawn volume is in no way a health risk for the subjects. Drawing of blood samples can leave the subjects with small hematomas and the patients will feel a small sharp scratch when the needle is inserted.

Adverse events

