The subjects will be questioned about adverse events during each study session and at the 24-hour plasma sample (as well as at 48 hours for the transdermal study session). We have defined five pre-specified self-reported symptoms (fatigue, confusion, depressed mood, or headache), based on the most commonly reported adverse reactions of melatonin available in the literature [See attached Investigators Brochure]. Volunteers will also be asked to report additional symptoms of adverse effect, if any. Both adverse reactions and adverse events will be reported in the CRF. An adverse reaction is defined as harm or unwanted reaction to a drug, no matter the dosage. An adverse event is defined as any medical event in a patient or healthy volunteer in a clinical trial after treatment with a drug, without any necessary connection between the treatment and the undesirable event.

Serious adverse events (SAE) are defined as any medical event that result in death, are life-threatening, lead to hospitalization, result in disability or permanent damage, or any other important medical event. All serious adverse events will be registered and reported to the Danish

Medicines Agency (Lægemiddelstyrelsen) and the Danish Committee on Health Research Ethics (Videnskabetisk Komité) in a final report.

Serious adverse drug reactions (SARs) will be reported annually (most likely irrelevant to this study, as it will not continue for a full year).

Suspected unexpected serious adverse reactions (SUSARs) will be reported immediately to the Danish Medicines Agency and the Danish Committee on Health Research Ethics.

Summary of Product Characteristics and Investigators Brochure (both are attached to this document) will be used to evaluate SUSARs. Adverse event registration will commence on the first study day and be finalized after the last study day. In case of serious adverse reactions the sponsor will decide if the study is to be terminated.

Setting

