The present procedures for quality control and assurance will be followed according to the EU GCP guidelines through planned and systematic agreements on monitoring before, during, and after the trial. A written authority for a third party (e.g. GCP monitor, the Danish Medicines Agency, etc.) for the access to medical records will be collected together with the informed, written consent.

Payment of participants

Participants will be paid DKK 150.00 every hour for the nine hours of study day 1-4, plus DKK 150.00 for each of the 24-hour blood samples. Participants will be paid DKK 150.00 every hour for the 17 hours of the transdermal study day, plus DKK 150.00 for the 24- and 48-hour blood samples. In total, the participants will be paid DKK 8,850.00. The participants will receive the entire DKK 8,850.00 upon finishing all five study-days and the 24- and 48-hour blood samples. Should a participant withdraw their consent or be excluded from the trial at any point, they will receive compensation corresponding to the amount of hours they have participated. There will be no reimbursement of transportation for the participants.

Ethics

The study will be performed in accordance with the Helsinki II declaration. Subjects will be included after oral and written consent. Subjects can withdraw from the study at any time without stating a reason. All information regarding participants in this study will be kept protected and no personal data will be published. The anonymity of all participants will be secured and data kept confidential. This study will only be initiated after approval from the ethics committee and the National Board of Health and will be carried out in accordance with the Helsinki declaration.

Risks and benefits of the study

There are minimal risks for the subjects, which are the discomfort of the five different routes of administration, as well as the plasma sampling, and the small risk of any adverse event.

The benefit of the study is clarification of the pharmacokinetics of melatonin when established rectally and intravesically. This knowledge is essential before studies investigating the radioprotective effects of locally administered melatonin in patients receiving ionizing radiation.

The benefit for the subjects is the financial compensation they receive, as described above.

Financing

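### Nausea and non-burning local irritation, the first named and the second implied as reactions to the DMSO vehicle, are captured only by an open question and not by the yes/no symptom list

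*Combined protocol and SAP*

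**What the plan says.** The Objective makes possible adverse reactions of each route part of the study aim, next to pharmacokinetics.

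Under Secondary outcomes, the symptoms to be asked about are "pre-specified self-reported symptoms of nervousness, confusion, depressed mood, dizziness, headache, garlic breath and burning sensation from application area (yes/no". The next sentence adds an open question: "Volunteers will also be asked to report additional symptoms of adverse reactions, if any (yes/no + description". Answers go into the CRF.

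The Adverse events section gives another list: "We have defined five pre-specified self-reported symptoms (fatigue, confusion, depressed mood, or headache". It says this list is "based on the most commonly reported adverse reactions of melatonin available in the literature", and it too adds an open question: "Volunteers will also be asked to report additional symptoms of adverse effect, if any". Questioning takes place during every session and at the 24-hour sample, and at 48 hours for the transdermal session.

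The section on adverse reactions of DMSO describes garlic-like breath and taste, then reports that "up to 48% of patients with interstitial cystitis reported adverse reactions, including urethral irritation and nausea". It describes these reactions as self-limiting, with a duration of up to 24 to 48 hours.

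The section on risks and benefits calls the risks minimal. It names the discomfort of the five routes, "as well as the plasma sampling, and the small risk of any adverse event".

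**The concern.** A yes/no checklist gives a recorded answer, positive or negative, for each item from each woman in each session. An open question gives an answer only for what the woman thinks to mention. If a reaction that the protocol itself expects from the vehicle is off the checklist, its absence cannot be told apart from its not being mentioned.

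This matters here because adverse reactions are part of the aim and will be described by route in only 8 to 10 women. One or two unrecorded cases would visibly change the description of a route. Three of the five formulations contain DMSO, so a list drawn from melatonin reactions alone does not fit them. The risk statement also does not carry forward the one incidence figure that the protocol gives for the vehicle.

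**Working it through.** The main check compares the lists item by item. The documents state no figure of their own to reproduce.

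**Step 1. DMSO exposure.** The intravesical dose is 50 ml of a 50% w/w DMSO solution (Study session 3). The rectal fluid is 2.5 ml with 40% w/w DMSO (Melatonin rectal fluid). The cream is 1 g with 150 mg/g DMSO (Melatonin cream). No DMSO is described for the intravenous solution or the suppository. That is 3 of 5 sessions.

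**Step 2. DMSO reactions against the two lists.**

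| Reaction named in the DMSO section | Secondary outcomes list | Adverse events list |
|---|---|---|
| Garlic-like breath or taste | Listed (breath) | Not listed |
| Urethral irritation | Only as burning at the application area | Not listed |
| Nausea | Not listed | Not listed |

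**Step 3. The lists against each other.** The first has seven items. The second announces five and names four. They share three: confusion, depressed mood and headache. Fatigue is only on the second. Nervousness, dizziness, garlic breath and burning are only on the first. If the CRF follows the second list, no DMSO or local reaction is solicited by name.

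**Step 4. What the open question records.** Under Secondary outcomes it is a single yes/no for any additional symptom, with a description. A no covers everything unlisted at once. A yes with some other symptom described leaves nausea unanswered. Neither gives a negative specific to nausea or to non-burning irritation.

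**Step 5. Scale, as illustration only.** Let p be the chance that a woman has any DMSO reaction in the intravesical session. The expected number is n × p, and P(at least one) = 1 − (1 − p)^n. The protocol gives n = 8 (completers) and n = 10 (enrolled). The 48% is its quoted upper figure for interstitial cystitis patients; the lower rates are assumptions.

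| p | Expected, n = 8 | P(at least one), n = 8 | Expected, n = 10 | P(at least one), n = 10 |
|---|---|---|---|---|
| 0.48 | 3.84 | 1 − 0.52^8 = 0.995 | 4.8 | 1 − 0.52^10 = 0.999 |
| 0.24 | 1.92 | 1 − 0.76^8 = 0.889 | 2.4 | 1 − 0.76^10 = 0.936 |
| 0.10 | 0.8 | 1 − 0.90^8 = 0.570 | 1.0 | 1 − 0.90^10 = 0.651 |
| 0.05 | 0.4 | 1 − 0.95^8 = 0.337 | 0.5 | 1 − 0.95^10 = 0.401 |

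These numbers say how likely a reaction is, not how many would be missed.

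**Step 6. Size of any under-reporting.** This needs a capture rate, and the documents give none. With p = 0.48 and n = 10, assumed capture of 100%, 75%, 50% or 25% gives 4.8, 3.6, 2.4 or 1.2 counted cases. The shortfall is then 0 to 3.6, and the assumption alone decides it. Even this range treats every reaction as unlisted, although some may be burning or garlic breath. No estimate is therefore offered.

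**The case against.** The strongest reply is that these symptoms are not ignored. Both sections actively ask for additional symptoms, in every session and again at 24 hours, and the secondary-outcome version records a description. Burning at the application area covers part of urethral irritation, and garlic breath shows that the first list was already extended for DMSO; only the Adverse events list is said to rest on melatonin reactions. All of this stands. A reader might infer that intravesical tolerability will be undercounted. The documents do not show that; they support only that under-reporting is possible.

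A reader might also take 48% as the rate of nausea and urethral irritation. It is the share with any adverse reaction, an upper figure from one study of patients with bladder disease. No separate rate for either symptom appears, and none is given for the listed symptoms, so nothing shows that the listed ones are rarer.

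Nor does the checklist single out the bladder route on nausea, because nausea is unlisted in every session. The protocol sets no tolerability rule for taking a route forward and plans no formal comparison of adverse reactions between routes.

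On the risk statement, a reader might infer a flat contradiction. That goes too far: the sentence acknowledges discomfort of the routes separately, the volunteers are healthy, and the DMSO reactions are described as self-limiting. What remains is a tension in wording.

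The reply does not remove Step 4: the open question leaves these vehicle reactions without a symptom-specific negative.

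**Conclusion.** The point holds as a gap in coverage. Nausea is on neither solicited list, and irritation or pain other than burning is on neither, although the protocol names nausea and urethral irritation as reactions to a vehicle used in three of the five sessions. They may be under-reported and will not be recorded on the same yes/no basis as the listed symptoms. That the two lists disagree, and that one of them has no DMSO or local item, adds to the gap.

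The size of any under-reporting cannot be computed. The probabilities in Step 5 assume that a single rate applies independently to each woman, and carrying 48% over to healthy women is itself an assumption. They show only that at least one reaction is a realistic prospect over the range considered, so the item is worth recording. At or near the quoted upper figure, the description of adverse-event risk as small would not suit the intravesical session; at 5% the tension is much weaker. This is a low-cost improvement to data collection and does not affect the pharmacokinetic analysis.

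**What to change.** 1. Use one solicited yes/no list, identical under Secondary outcomes, under Adverse events and in the CRF. Reconcile the existing items, including the count of five against four named.
2. Add nausea, and irritation or pain at the application site, worded by site: urethra/bladder, anus/rectum, vagina, skin. Ask the whole list in all five sessions so that routes are described on the same basis. Keep the open question for anything else.
3. Reword the risk sentence under Risks and benefits to agree with the DMSO section. Cite the figure of up to 48% as any adverse reaction in interstitial cystitis patients, say that the rate in healthy women is unknown, and state that the reactions are reported as self-limiting with a duration of up to 24 to 48 hours.

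The cost is a few extra checklist lines per session and one rewritten sentence. Nothing changes in sample size, blood sampling or analysis. The list must be settled before the first session, because negatives that were not asked for cannot be recovered reliably afterwards.

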
will be drawn as “waste”, to ensure that the following 6 ml consist of undiluted blood, totaling another 52 ml of blood. In total, the subjects will have 136 ml of blood samples each study session.

For the transdermal study session, blood samples are drawn at baseline, 0 min, 30 min, 1 hour, 2 hours, 4 hours, 6 hours, 8 hours, 10 hours, 12 hours, 16 hours, 24 hours and 48 hours. Intervals are based on data from previous pharmacokinetic studies of transdermal melatonin [23]. Blood samples are drawn from a peripheral venous catheter within the first 16 hours, and the 24- and 48-hour samples will be sampled through a single venipuncture each. Each plasma sample will have a total volume of 6 ml, totaling 78 ml for the transdermal study session. For the blood samples drawn from a peripheral venous catheter, 4 ml of blood will be drawn as “waste”, to ensure that the following 6 ml consist of undiluted blood, totaling another 44 mL of blood. In total, the subjects will have 122 ml of blood drawn samples for the transdermal study session.

Plasma samples will be kept in a locked freezer (with a temperature-alarm) at the Department of Surgery, Herlev Hospital. The plasma concentration will be assessed by radioimmunoassay (RIA)-technique at Gastrolab, Herlev Hospital. RIA-technique is a validated method of determining melatonin in plasma that has been used for years [28]. A bio-bank will be created, containing solely the plasma samples from this study (see Data Management for further details). In the case report forms (CRF), the collection time of each sample will be noted. The plasma concentrations will be delivered to the investigator digitally from the laboratory, and will afterwards be noted in the through double entry CRF, by independently two investigators.

Secondary outcomes

Sedative effects and other adverse effects

A Karolinska sleepiness scale (KSS)-score will be performed at baseline and once every hour for 8 hours, as well as at 24 hours, and noted in the CRF. For the transdermal study session, the score will

be performed at every hour on the first day until 16 hours, as well as at 24 and 48 hours. The KSS is frequently used to evaluate subjective sleepiness. The scale has been validated against performance and EEG-variables [29].

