A study administered 1 g of melatonin orally to patients for 25-30 days, with drowsiness as the only adverse reaction [37]. These patients had substantial clinical tests (hematological and blood chemistry tests, urine analysis, heart rate and blood pressure monitoring and ECG) performed, and no reactions to melatonin were demonstrated [37]. Another study investigated the effect of intravenously administered melatonin in healthy subjects, as well as patients with Parkinson's disease and epilepsy. They applied 1.25 mg/kg melatonin as a bolus injection. One of the patients, who had 1.25 mg/kg melatonin intravenously, received further two doses of 0.5 mg/kg. Correspondingly, melatonin was non-toxic and no adverse reactions were observed [38].

Furthermore, melatonin has been used as an intravenous infusion in neonates with sepsis, in neonates undergoing abdominal surgery, and in preterm infants [6, 39, 40]. A total of 224 patients were included (of whom 105 received melatonin). No adverse reactions were reported at a dose of 10 mg/kg intravenously [6, 39, 40].

Melatonin has also been given in very large doses up to 100 mg intravenously in adults, without adverse reactions [5]. Other studies investigated melatonin when used as a pre-medication for gynecological laparoscopic surgery, and demonstrated no adverse reactions at a dose of 5-20 mg of sublingual melatonin [41, 42]. No adverse reactions were reported in a study investigating pre-medication with 5 mg melatonin prior to laparoscopic cholecystectomy [43].

Drowsiness, confusion and depression have been described as adverse reactions of melatonin in a study examining whether melatonin could augment antidepressant treatment in patients with depression [44]. Furthermore, a few studies report headache [45] and fatigue as side-effects of melatonin [46].

A comprehensive review of the safety of melatonin concludes that no studies have indicated that exogenous melatonin should induce any serious reactions effects [47]. Long-term safety of melatonin in children and adolescents requires further investigation. Due to a lack of studies, pregnant and breast-feeding women should refrain from taking exogenous melatonin [47].

Adverse reactions of DMSO

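### The sleep-disorder and mental-illness exclusions are defined by treatment alone, so diagnosed but untreated women are not excluded, and the yes/no symptom reports have no pre-dose record to separate out their symptoms

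*Combined protocol and SAP*

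**What the plan says.** Under Subjects/population, two exclusion criteria carry a definition in brackets: "Known and diagnosed sleep-disorder (defined as being in current medical treatment") and "Mental illness (defined as being in medical treatment"). Two neighbouring exclusions bear on the same women: "Current use of melatonin or other hypnotics/sedatives", and "Serious comorbidity (American Society of Anesthesiologists (ASA) physical status 3-4"). The first inclusion criterion is "Healthy female". The protocol does not define healthy, and it describes no screening for sleep or mental health.

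The section on withdrawal and dropout makes a subject a dropout if she comes to meet an exclusion criterion during the study. It also says that dropouts' data are not analysed.

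Under Secondary outcomes, "A Karolinska sleepiness scale (KSS)-score will be performed at baseline and once every hour for 8 hours, as well as at 24 hours". Reaction time is also tested at baseline and hourly. Other adverse reactions are "pre-specified self-reported symptoms of nervousness, confusion, depressed mood, dizziness, headache, garlic breath and burning sensation from application area (yes/no"). The Adverse events section gives a somewhat different list, which adds fatigue. No time before dosing is stated for any of these yes/no items.

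All five sessions give melatonin. The Statistics section plans descriptive summaries and pharmacokinetic parameters. It gives no specific analysis for the sleepiness, reaction-time or symptom data.

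**The concern.** Each bracket narrows the criterion it explains. A sleep disorder that is known and diagnosed but not under treatment does not meet its exclusion as defined, and the same holds for mental illness. Yet these disorders can produce the symptoms the trial counts as possible reactions to melatonin. The protocol makes the link itself: "Drowsiness, confusion and depression have been described as adverse reactions of melatonin", in a study of patients treated for depression.

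The stated aim covers adverse reactions as well as pharmacokinetics, by route, in at most ten women. In so small a sample one subject's standing symptom is a visible share of any reported rate. With neither a placebo session nor a pre-dose symptom record, nothing in the data would show that it was there beforehand.

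The protocol already guards against disturbed sleep by excluding recent and planned night-shift work. Leaving out untreated diagnosed sleep disorders does not fit well with that.

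**Working it through.** **1. Who is barred.** The plan gives no figure to reproduce here, so the first step is to set the criteria side by side for a woman with a diagnosed, untreated disorder.

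| Criterion | Does it bar her? |
|---|---|
| Sleep disorder, as defined | No: she is not in treatment |
| Mental illness, as defined | No: she is not in treatment |
| Use of melatonin, hypnotics or sedatives | No: she takes none |
| ASA 3-4 | Not clearly: milder comorbidity is not excluded |
| Healthy (inclusion) | Undetermined: the term is undefined |
| Dropout rule | No: it is triggered by the exclusion criteria, so a diagnosis made during the study does not count until treatment starts |

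The separate power to remove a subject is tied to her safety, so it is not a general route for excluding her.

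**2. Weight of one subject.** Ten women are included and the study may conclude with eight completers, so n is 8 to 10.

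- Share of the sample: 1/10 = 10%; 1/8 = 12.5%.
- If she answers yes to a symptom because of her disorder and would otherwise answer no, that symptom's rate for one route rises by 10 to 12.5 percentage points.
- If the symptom is present in all five sessions, the pooled rate rises by the same amount: 5/50 = 10%; 5/40 = 12.5%.
- If it is stable, it adds equally to every route, so differences between routes do not move. The absolute rates do.

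**3. Sleepiness score.** Suppose she scores d points above what she would score without the disorder.

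- Raw mean: the shift is d/n. For an assumed d of 2 to 4 and n = 8, that is 2/8 = 0.25 to 4/8 = 0.5 points.
- Change from session baseline: the shift is (d − d)/n = 0 if the offset is stable.

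The assumed d has no source in the documents. The sentence giving the transdermal schedule does not repeat the word baseline; I take the general baseline assessment to apply there too.

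**4. Chance that she is enrolled.** The documents give no prevalence of untreated diagnosed disorder among women who would volunteer. With independent volunteers and an assumed prevalence p, the chance of at least one is 1 − (1 − p)^n:

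| Assumed p | n = 8 | n = 10 |
|---|---|---|
| 1% | 7.7% | 9.6% |
| 2% | 14.9% | 18.3% |
| 5% | 33.7% | 40.1% |
| 10% | 57.0% | 65.1% |

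The range is wide because p is unknown. It shows only that the event need not be rare.

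**The case against.** The strongest reply is that failing to meet an exclusion does not make a woman eligible. She must also be healthy, and an investigator could refuse someone with diagnosed depression or narcolepsy on that ground. This stands against the tempting reading that such women are eligible: the documents support only that they are not excluded and that the decision is left to judgement. It does not close the gap. Healthy is undefined, only ASA 3-4 is excluded for comorbidity, and where the protocol does say what counts as a sleep disorder or mental illness, it says treatment.

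A second reply is that treatment status is simple to check and that medical treatment need not mean medicines. That is fair. The status of psychotherapy alone is unclear, and I do not claim that it is admitted.

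A third is that the crossover and the session baselines remove a stable offset. For sleepiness and reaction time the data for this are collected, although the plan does not commit to analysing change from baseline. Session order is fixed, so a fluctuating disorder would not separate from route. The reply does not reach the yes/no symptoms, which have no stated baseline.

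A fourth is that the Adverse events section defines an event as arising after treatment, so a symptom already present clearly meets neither the event nor the reaction definition. It would therefore be too strong to say that such symptoms will be recorded as effects of melatonin. They could be, because the items are listed as adverse reactions and no pre-dose answer exists to sort them.

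A reader might also infer that an altered sleep-wake rhythm distorts the measured melatonin concentrations. The documents give no figure for this, a baseline plasma sample is taken in every session, and night-shift work is excluded.

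**Conclusion.** The point holds in limited form. As defined, the two criteria do not exclude women with a diagnosed but untreated sleep disorder or mental illness, and their entry turns on an undefined word. What is exposed is the descriptive secondary safety data, chiefly the yes/no reports of nervousness, confusion and depressed mood. One such woman could add 10 to 12.5 percentage points to a reported symptom rate. This assumes that she is enrolled, that she has the symptom on the day, and that it is not recognised as pre-existing. The probability of the first is unknown.

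No effect on the pharmacokinetic primary outcome is shown. This is an inexpensive improvement to who is enrolled and how symptoms are attributed, not a flaw that undermines the study.

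**What to change.** Remove the two brackets and state the criteria by diagnosis: *known or diagnosed sleep disorder, whether or not treated* and *current diagnosed mental illness, whether or not treated*. The dropout rule refers to the exclusion criteria, so it follows without further change.

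Also record the yes/no symptoms before each administration, and count as possible reactions only those that are new or worse afterwards. This is the more general protection, because it also covers undiagnosed complaints and an ordinary headache or low mood in any volunteer.

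The cost is two lines of wording and one short set of questions per session. A few volunteers who might otherwise have entered are lost, which matters little when ten are needed. The real downside is that a woman newly diagnosed during the study would become a dropout and her data from completed sessions would not be used. The sponsor should accept this knowingly, given that the study needs at least eight completers.
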